Adjudication Process (For Attacks Occurring During the OLP)

The data generated during the Assessment Visit and the full assessment of the potential attack will be provided to the AC and follow the same process as described above for the RCP.

The data to be adjudicated will be provided to the independent AC by the vendor according to the Adjudication Committee Charter (see Section 4.3.1.5).

Regardless of the decision made by the AC, the subject may choose to continue in the OLP or withdraw from the OLP and enter the SFP.

All MRI scans are to be performed at the study site. To ensure that MRI scans are of acceptable quality for viewing the optic nerve, spinal cord, and brain, the settings and procedures (specified by the central reader) to be used for the MRI scanners are mandated at a minimum standard and defined in the MRI Imaging Manual (provided separately). The site will be required to perform a qualification MRI scan to send to the central reading site to ensure compliance with the requirements for the study. Qualification MRI scans may require consenting a volunteer subject from the investigative site, depending on local Institutional Review Board/Ethics Committee (IRB/EC) requirements.

All MRI images from the site will be date and time stamped and sent to the central imaging vendor that is independent of the study sites. The images will be read by 2 independent neuro-radiologists at the central reading site for a consensus read and central reporting. The MRI reports and scans produced as part of the protocol-defined criteria for an NMO/NMOSD attack will be sent from the central reading site to the AC as part of the assessment data to be adjudicated.

4.3.1.3 Independent Ophthalmology Assessments

The protocol-defined ophthalmology assessment will consist of a high- and low-contrast visual acuity test, and assessment for relative afferent pupillary defect (RAPD).

All examinations must be conducted by an ophthalmologist or another site member with appropriate training and experience who is independent of the investigator and the subject. If possible, the same person should review a single subject through every ophthalmology assessment. The data generated from the ophthalmology assessments will be entered directly into an electronic data capture device provided to the site with a date and time stamp. In order to minimize bias, the ophthalmology examiner will not have access to prior visual acuity scores or RAPD findings at the time of a new evaluation. The ophthalmology examiner will be instructed NOT to elicit or discuss the subjects' experiences or AEs on the study.

Ophthalmology assessments will be completed at screening, Day 1, at scheduled study visits, and Assessment Visits, according to the schedule of procedures in Table 5, Table 6, Table 7, Table 8, and Table 9.

In the event that a subject has new or worsening symptoms related to NMO/NMOSD, all ophthalmology assessments will also be performed at an Assessment Visit.

The ophthalmology examiner will provide a full report of the examination findings, in accordance with protocol-defined parameters, to the investigator to review against a subject's

previous reports and to determine if the findings meet 1 or more of the protocol-defined criteria for ON attack.

Visual Acuity Assessments

For the purposes of this study, visual acuity will be measured using Landolt C Broken Ring Chart (both high and low contrast). Best-corrected monocular and binocular vision will be tested.

Visual acuity tests are used to determine the smallest characters that can be read on a standardized chart. The Landolt C Broken Ring Chart has a standardized format designed to be equally detectable for normal observers consisting of an incomplete ring resembling the letter "C." The width of the break and the ring are each one-fifth of its overall diameter. The subject must indicate where the break is located, the break being positioned in any direction. Each line has 5 rings and the spacing between the rings and the lines is proportional to the ring size. The change in visual acuity from one line to the next occurs in equal logarithmic steps.

To standardize the method of assessment, the charts must be used in a retro-illuminated Early Treatment Diabetic Retinopathy Study (ETDRS) cabinet to eliminate the need for standardization of height and room lighting.

Charts and wheeled light cabinets will be supplied to all sites.

To ensure consistency of visual acuity testing across subjects and study sites, the following set-up and procedures are required:

Low-contrast Visual Acuity

- Charts must be used with a retro-illuminated ETDRS cabinet
- Use a well-lit room, but one not exposed to full sunlight to not distract from the subject's normal eyesight
- Use overhead lights to provide an even distribution of light across the room
- Prevent distractions and limit movement in the room
- Position the subject at a distance of **3 meters** from the chart
- Test best-corrected monocular and binocular vision
- Ask the subject to describe the top line of the chart from left to right. Record the number of rings that the subject successfully describes as the subject describes them. If subject cannot easily read the rings, ask the subject to guess.
- Ask the subject to continue reading each subsequent line below the top line until the subject reaches a line where all the rings cannot be made out. Record the number of rings that the subject successfully describes as the subject reads them
- Compare the subject's results against the actual rings on each line of the chart
- The last line the subject is able to see and read correctly determines the score

High-contrast Visual Acuity

- Use a well-lit room, but one not exposed to full sunlight to not distract from the subject's normal eyesight
- Use overhead lights to provide an even distribution of light across the room
- Prevent distractions and limit movement in the room
- Position the subject at a distance of **3 meters** from the chart
- Test best-corrected monocular and binocular vision
- Ask the subject to describe the top line of the chart from left to right. Record the number of rings that the subject successfully describes as the subject views them. If subject cannot easily read the rings, ask the subject to guess.
- Ask the subject to continue describing each subsequent line below the top line until the subject reaches a line where all the rings cannot be made out. Record the number of rings that the subject successfully describes as the subject reads them
- Compare the subject's results against the actual rings on each line of the chart
- The last line the subject is able to see and read correctly determines the score

The following visual acuity data are to be reported by the ophthalmology examiner:

- Low-contrast visual acuity score for each eye separately and both eyes together
- High-contrast visual acuity score for each eye separately and both eyes together
- If a subject cannot read any lines on the chart, visual acuity will be tested by counting fingers (CF), hand movement (HM), or light perception (LP) at 1 meter, or no light perception (NLP)/total blindness.

Assessment of Relative Afferent Pupillary Defect

For the purposes of this study, RAPD will be assessed by the "swinging light test," a method of detecting differences between the two eyes in how the pupils respond to light shone in one eye at a time. This test must be administered by an ophthalmologist or another site member with appropriate training and experience (ie, not the investigator) and in accordance with standard of care at the institution. If possible, the same ophthalmology examiner should review a single subject through every assessment.

The RAPD test can be useful in detecting unilateral or asymmetric disease of the retina or optic nerve. The physiological basis of the test is that in healthy eyes the reaction of the pupils in the left and right eyes are linked; that is, a bright light shone in one eye will lead to equal constriction of both pupils. A RAPD is present if the initial consensual pupillary constriction is greater than the initial direct pupillary constriction.

The following procedures are recommended:

- Perform the test in a semi-darkened room. If the room is too dark it will be difficult to observe pupil responses, particularly in heavy pigmented eyes
- Use a bright torch such as a small flashlight that can be focused to provide a narrow, even beam of light
- Ask the subject to focus on a distant object and keep looking at it – use a chart or picture as an object of focus
- Move the flashlight from side to side so the beam of light shines directly into each eye. Do not swing the beam from side to side around a central axis (eg, by holding it in front of the subject’s nose) as this can stimulate the near response
- Keep the light source at the same distance from each eye to ensure the light stimulus is equally bright in both
- Keep the beam of light steadily on the first eye for at least 3 seconds to allow the pupil size to stabilize. Note whether the pupil of the eye being illuminated reacts briskly and constricts fully to the light. Also note the response in the other eye – does it also constrict briskly?
- Move the light quickly to shine in the opposite eye. Hold the light steady for at least 3 seconds. Note whether the pupil of the eye being illuminated stays the same size, or whether it gets bigger. Note the response in the opposite eye.
- Repeat the test, observing the response of the pupils of both eyes when one and then the other is illuminated.

The RAPD results will be reported as follows:

- Date and time of examination
- Presence or absence or loss of RAPD in either eye
- If RAPD is present, record pupillary responses on a scale of 1+ to 5+ for each eye according to the criteria in Table 12.

Table 12 Pupil Response Scoring Criteria for Relative Afferent Pupillary Defect

Score	Definition
1 +	Weak initial constriction and greater re-dilatation
2 +	Initial stall and greater re-dilatation
3 +	Immediate pupillary dilatation
4 +	Immediate pupillary dilatation following prolonged illumination of the good eye for 6 seconds
5 +	Immediate pupillary dilatation with no secondary constriction

Source: [Bell et al, 1993](#).

On receipt of the full examination results from the ophthalmology examiner, the investigator must compare the results against the last assessment.

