Visual loss and dysfunction are recognized disabling clinical manifestations in patients with NMO/NMOSD. In MS clinical trials, low-contrast visual acuity emerged as the leading candidate to measure visual disability in MS. Subsequent studies found that low contrast acuity testing correlated well with brain MRI lesion burden, visual evoked potentials and retinal nerve fiber layer (RNFL) loss as measured by optical coherence tomography (OCT). Worsening of visual function by a clinically significant > 7 letters or approximately 1.5 lines for low-contrast acuity is associated with approximately 4.5 μm reduction in RNFL thickness in MS. Additional longitudinal studies have shown RNFL axonal loss over time that occurs even in the absence of an acute ON attack and correlates with clinical meaningful worsening of vision and quality of life in patients with MS. The low-contrast visual acuity test is used to determine the number of letters that can be read on a standardized low-contrast Landolt C Broken Rings Chart held at a distance of 3 meters. Due to lack of standard visual function measures specific to NMO/NMOSD, and the fact that both MS and NMO/NMOSD patients can experience ON, and this endpoint has been previously used widely in MS studies, there is good rationale for using this endpoint in this NMO/NMOSD study. This secondary endpoint will evaluate whether MEDI-551 will have an effect on improving vision sensitivity.

Reduction in the Cumulative Total Active MRI Lesions (New Gd-enhancing or New/Enlarging T2)

In clinical practice there is wide use of MRI in the diagnosis and management of NMO; however, the role of MRI in this setting is not well established and studied. The actual interpretation of MRI related to the diagnosis and the follow up of patients with NMO/NMOSD are not consistently established. Therefore, this study aims to collect longitudinal MRI data during both study periods including at the time of an attack, to investigate the characteristics and evolution of spinal and brain lesions in NMO/NMOSD.

Number of NMO/NMOSD-related In-patient Hospitalizations During the Randomized-controlled Period

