Blurred vision Loss of vision Eye pain	ON	
 1. Greater than 15-character drop in high-contrast Landolt C Broken Rings Chart from last visit as measured in a previously affected eye and no other ophthalmological explanation 2. At least 2-step drop ^c in CF to NLP from last visit as measured in a previously affected eye and no other ophthalmological explanation 3. At least 7 or more character drop in low-contrast Landolt C Broken Rings Chart from last visit as measured in either eye alone (monocular) AND a new RAPD in affected eye 4. At least 7 or more character drop in low-contrast Landolt C Broken Rings Chart from last visit as measured in either eye alone (monocular) AND loss of a previously documented RAPD in fellow eye 5. At least 5 or more character drop in high-contrast Landolt C Broken Rings Chart from last visit as measured in either eye alone (monocular) AND a new RAPD in affected eye 6. At least 5 or more character drop in high-contrast Landolt C Broken Rings Chart from last visit as measured in either eye alone (monocular) AND loss of a previously documented RAPD in fellow eye 7. At least 1-step drop ^d in CF to NLP from last visit as measured in a previously affected eye AND a new RAPD in affected eye 8. At least 1-step drop ^d in CF to NLP from last visit as measured in a previously affected eye AND loss of a previously documented RAPD in fellow eye 9. At least 7 or more character drop in low-contrast Landolt C Broken Rings Chart from last visit as measured in either eye alone (monocular) AND a new Gd-enhancing or new/enlarging T2 MRI lesion in the corresponding optic nerve ^f 10. At least 5 or more character drop in high-contrast Landolt C Broken Rings Chart from last visit as measured in either eye alone (monocular) AND a new Gd-enhancing or new/enlarging T2 MRI lesion in the corresponding optic nerve ^f 11. At least 1-step drop ^d in CF to NLP from last visit as measured in a previously affected eye AND a new Gd-enhancing or new/enlarging T2 MRI lesion in the corresponding optic nerve ^f
Deep or radicular pain Extremity paraesthesia Weakness Sphincter dysfunction	Myelitis ^e	
 12. At least 2-point worsening in 1 or more of the relevant (pyramidal, bladder/bowel, sensory) FSS compared to last visit 13. At least 1-point worsening in EDSS score compared to last visit if previous EDSS score is 5.5 or more

Table 11 Protocol-defined Criteria for an NMO/NMOSD Attack

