4.6.3 Methods for Reducing Bias

The following steps are being planned to mitigate/reduce bias towards the assessment of an NMO/NMOSD attack:

- 1 Study subjects will be instructed not to discuss AEs or NMO/NMOSD-related symptoms/medications with any of the independent assessors.
- 2 The EDSS rater will not have access to prior EDSS scores/FSS at the time of a new evaluation and will perform the evaluation of the subject without any knowledge of the subject's AE history or management of symptoms or findings from physical/neurological

examinations. The EDSS rater will be instructed NOT to elicit or discuss the subjects' experiences or AEs on the study. The EDSS rater must not manage the subject outside of the protocol for routine care or any other purpose. The EDSS scores will be captured electronically and transmitted to the investigator who will have access to the scores to compare against the protocol-defined criteria for an NMO/NMOSD attack. The EDSS scores/FSS will be monitored centrally by an independent expert.

- 3 The ophthalmology examiner will not have access to prior visual acuity and RAPD at the time of a new evaluation and perform the evaluation of the subject without any knowledge of the subject's AE history or management of symptoms or findings from physical/neurological examination. The ophthalmology examiner will be instructed NOT to elicit or discuss the subjects' experiences or AEs on the study. The ophthalmology examiner must not manage the subject outside of the protocol for routine care or any other purpose. The visual acuity scores and RAPD findings will be captured electronically and transmitted to the investigator who will have access to the score to compare against the protocol-defined criteria for an NMO/NMOSD attack.
- 4 The neuro-radiologist will not have access to the subject's AE history or management of symptoms or findings from physical/neurological examination.
- 5 To minimize the potential influence of MRI findings on clinical assessment of possible attacks, MRI images/study report should not be reviewed by the Principal Investigator unless a specific criterion for an attack requires review of the MRI. In such cases, review of the MRI image and local study report MUST be done AFTER all relevant clinical assessments are completed. The time sequence of all procedures and reviews required for assessment will be documented to demonstrate compliance.

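### The last-line rule for scoring visual acuity does not fit the character counts that the optic-neuritis criteria and key secondary endpoint 2 rely on

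*Protocol*

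**What the plan says.** **The scoring rule.** Protocol section 4.3.1.3 gives a list of steps for each chart. Both lists end with the same bullet: "The last line the subject is able to see and read correctly determines the score". The same section states "Each line has 5 rings". Earlier in each list the examiner is told to count; the low-contrast wording is "Record the number of rings that the subject successfully describes as the subject describes them". When the section then lists the acuity data to be reported, it names only low- and high-contrast scores (each eye and both eyes), plus the finger-counting to no-light-perception steps for subjects who cannot read any line.

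**What the score is used for.**
- Protocol Table 11 (repeated in SAP Table 3.4.1.4-1) sets criteria 3, 4 and 9 as "At least 7 or more character drop in low-contrast Landolt C Broken Rings Chart from last visit as measured in either eye alone (monocular"), criteria 5, 6 and 10 as a high-contrast drop of at least 5 characters, and criterion 1 as a high-contrast drop of more than 15.
- Protocol section 3.2.4.2, the rationale for key secondary endpoint 2, says the low-contrast test is "used to determine the number of letters that can be read on a standardized low-contrast Landolt C Broken Rings Chart". It also gives a conversion: "Worsening of visual function by a clinically significant > 7 letters or approximately 1.5 lines for low-contrast acuity".
- SAP sections 3.4.2.1 and 3.4.2.3 analyse the change in binocular low-contrast score by ANCOVA and give no unit.
- SAP Appendix 4, Table 7-8, bands high-contrast acuity in characters (50 or more, 35-49, 20-34, 1-19).

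**What reaches the investigator.** Section 4.3.1.3 says "The ophthalmology examiner will provide a full report of the examination findings", and that the investigator compares the full results with the last assessment. Section 4.6.3 says the acuity scores go to the investigator, "who will have access to the score to compare against the protocol-defined criteria for an NMO/NMOSD attack".

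**The concern.** A score fixed by the last line read moves in whole lines. The thresholds of 7 and of more than 15 characters fall between line boundaries, and the threshold of 5 equals exactly one line, so a subject on a boundary can cross it by losing a single ring. No sentence in either document turns a line into a number of characters. An examiner who follows the bullet and one who totals the rings could therefore report different drops for the same eye.

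Two uses matter most. The acuity drop is one component of the optic-neuritis criteria that feed the primary endpoint, and the binocular low-contrast score is a key secondary endpoint under Type I error control. The point also remains live for open-label assessments, because protocol section 3.1.1.4 has attacks followed there in the same way.

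**Working it through.** **1. The protocol's own conversion.** With 5 rings per line, 7/5 = 1.4 lines and 8/5 = 1.6 lines. This reproduces the stated equivalence of more than 7 letters with about 1.5 lines. That equivalence needs resolution finer than one line, which a last-line score does not have.

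**2. A literal line number.** If the score were simply the number of the last line, a drop of 7 would mean seven lines, and in Table 7-8 any line number from 1 to 19 would fall in the 1-19 band. The character thresholds could not be applied as intended.

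**3. An illustrative conversion.** Suppose the score is 5 x complete lines, reading is sequential, and the five start positions within a line are equally likely. The documents state none of these. For start position s and true drop d in rings:

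registered drop = 5 x floor(s/5) - 5 x floor((s - d)/5)

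Possible registered drops are 0, 5, 10, 15, 20 and so on. Hence at least 7 acts as at least 10, and more than 15 acts as at least 20.

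| Acuity threshold | True drop (rings) | Share of start positions registering as met |
|---|---|---|
| At least 7, low contrast | 6 / 7 / 8 / 9 / 10 | 1/5, 2/5, 3/5, 4/5, 5/5 |
| More than 15, high contrast | 16 / 17 / 18 / 19 / 20 | 1/5, 2/5, 3/5, 4/5, 5/5 |
| At least 5, high contrast | 1 / 2 / 3 / 4 | 1/5, 2/5, 3/5, 4/5 |

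The discrepancy runs in both directions. These are shares for the acuity component only and are not attack misclassification rates.

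**4. Fallback between criteria.** Criteria 3, 4 and 9 carry the same second conditions as 5, 6 and 10. A missed low-contrast threshold can therefore still qualify if high-contrast acuity falls in the same eye. For a true low-contrast drop of 7, with start positions on the two charts independent, the share meeting one or other acuity threshold is 1 - (1 - 0.4) x (1 - p), where p is the share of positions in which the high-contrast drop registers as at least 5. It is 0.40 with no high-contrast loss, 1 - 0.6 x 0.4 = 0.76 with a 3-ring drop, 1 - 0.6 x 0.2 = 0.88 with 4, and 1.00 with 5 or more. A fallback can change the descriptive criteria-based severity, because SAP Table 3.4.1.4-1 grades 5, 6 and 10 as mild, 3, 4 and 9 as moderate, and 1 as severe.

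**5. Endpoint 2.** Rounding down within a line gives an error spread evenly over 0 to 4 rings, with variance (25 - 1)/12 = 2. Two assessments give 2 + 2 = 4, an SD of 2 rings per change score. The mean registered drop equals the true drop: for a true 7 it is 0.6 x 5 + 0.4 x 10 = 7. In simulation, true arm differences of 1, 2, 3 and 5 rings were recovered as 1.00, 2.00, 3.00 and 5.00. The standard error rises by about sqrt(1 + 4/SD^2) - 1. For assumed SDs of true change of 5, 8, 10 and 15 rings (the documents give none), this is 7.7%, 3.1%, 2.0% and 0.9%; simulating the ANCOVA gave 7.6%, 3.1%, 1.9-2.0% and 0.8-0.9%.

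**6. Table 7-8.** The cut points 20, 35 and 50 are multiples of 5, so 5 x complete lines gives the same band as the ring count except at 1 to 4 rings, which would become 0 and fall in no band.

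**The case against.** The strongest reply is that the documents point to one intended unit and contain one loosely worded bullet. The Amendment 3 entry in protocol section 9 says text was added to clarify when the acuity tests should stop, so the bullet may be a stopping rule: the last readable line ends the count. Examiners are told to record rings and check them against the chart, which would serve little purpose if only the last line counted. Section 3.2.4.2 is itself a competing definition for the low-contrast test, so the bullet is not the only statement of what is measured. The investigator sees full results, and device settings and site training, which are not in these documents, may have settled the matter.

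Much of this stands. A ring count was probably intended, and the data for it may exist. It does not remove the conflict. The bullet before the disputed one already says when to stop. The disputed bullet says what determines the score, and scores are what the section lists for reporting and what section 4.6.3 passes on for comparison with the criteria.

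It is also fair to object that every share and percentage above rests on a conversion the documents never state. Subjects are told to guess, so errors need not fall only on the last line. The figures illustrate a mechanism and do not estimate what happened.

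**Conclusion.** The scoring rule is wrong as written. It conflicts with the letter count in section 3.2.4.2 and with the character thresholds of criteria 1, 3 to 6, 9 and 10. The documents do not show which value was used.

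A reader might infer more than this supports:
- *That attacks were misclassified, or that the hazard ratio or the 67 events are affected.* This cannot be computed. Criteria 3 to 6, 9 and 10 also need a change in relative afferent pupillary defect or an MRI lesion. Criterion 1 needs a previously affected eye with no other ophthalmological explanation. Fallbacks exist, and the Adjudication Committee applies its own judgement (section 4.3.1.5).
- *That endpoint 2 is biased or its Type I error inflated.* Under the illustrative conversion the effect is added noise, SD about 2 rings per change score, with no expected bias between masked arms.
- *That Table 7-8 fails.* The problem there is mainly the unit. Numerically it arises only at 1 to 4 rings, in a scale the SAP calls exploratory.

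Confidence is high that the texts conflict. The practical size is unknown until the capture device output is checked.

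**What to change.** In the SAP, define the acuity score for endpoint 2, for criteria 1, 3 to 6, 9 and 10, and for Table 7-8 (high contrast) as the total number of rings correctly identified, per eye or binocular as applicable. Replace the last-line bullet in both protocol lists with the same definition, so that open-label assessments follow it too.

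Before unmasking, confirm which value the capture device produced. Only if it was a line score, re-derive endpoint 2 from the recorded ring counts and list the acuity-based determinations that differ, leaving Adjudication Committee determinations unchanged in the primary analysis. If ring counts were not kept, say so in the SAP and report the thresholds as they were applied.

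The cost is one SAP definition, one protocol bullet changed in two places, and a masked check of the device output. No new assessment is needed.
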